# Additional test:

Null and alternative hypotheses:

$$H_0: AUC_1 - AUC_2 = 0$$
$$H_0: AUC_1 - AUC_2 \neq 0$$

where  $AUC_1$  – the area under curve in the Product group,

CONFIDENTIAL

<sup>6 Performed using the SAS software. Assessment of the parameters for distributions – refer to p.2

AUC2 – the area under curve in the Placebo group;

the sample size for statistical tests was calculated using the following formula:

$$\mathbf{n}_1 = \mathbf{k}\mathbf{n}_2$$
$$\mathbf{n}_2 = \frac{\left(z_{\alpha/2} + z_\beta\right)^2 * (1 + 1/k) * \sigma^2}{\varepsilon^2}$$

where  $n_1$ ,  $n_2$  – the sample size of the study drug and the placebo groups respectively;

 $\varepsilon = AUC_1 - AUC_2$  – the expected difference in the severity AUC between the Product and Placebo groups;

**k** – the ratio of choice between Product and Placebo (1 to 1);

 $\sigma$  – the standard deviation of the AUC;

 $z_{\alpha/2}$  – a tabulated two-tailed z-test for  $\alpha$ ;

 $z_{\beta}$  – a tabulated one-tailed z-test for  $\beta$ .

1.8 final sample size will be determined using the formula:

 $N_T = N_{PP} / (1 - C_w),$ 

where  $N_T$  – the final sample size;

 $N_{PP}$  – the value calculated in section 1.8, i.e. the expected number of the subjects completing the study per protocol;

 $C_w$  – withdrawal coefficient.

2. Assumptions about the expected effects of the clinical study.

Time to resolution of symptoms in the Product group is 5.18 days, time to resolution of symptoms in the Product group is 5.84 days.

A priori estimates for tested parameter variables in the groups

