# Secondary endpoints

- 1. ARVI severity (clinically diagnosed and/or PCR-confirmed); based on the area under the curve (AUC) data for the Total Severity (TS) score on days 1-6 of the observation).
- Percentage of patients with resolution of ARVI symptoms (clinically diagnosed and/or PCRconfirmed).
- 3. Time to resolution of ARVI symptoms (PCR-confirmed).
- 4. Percentage of patients with resolution of ARVI symptoms (PCR-confirmed).
- 5. Dosing frequency of antipyretics on days 1-3 of therapy.
- 6. The percentage of patients requiring administration of antibiotics during 4-7 days of the observation

<sup>1 Time from enrollment to symptom resolution. **Criteria of resolution of ARVI symptoms:** body/axillary temperature  $\leq$ 37.3oC for 24 hours (without subsequent increase within the observation period) + absence/presence of general ARVI symptoms with  $\leq$ 2 point of Total Severity (TS) score.

<sup>2 Total Severity (TS) index will be calculated from the rating scores obtained for each of the symptoms of ARVI (body temperature, non-specific/flu-like symptoms, and nasal/throat and chest symptoms); the subsequent data analysis will be performed by Materia Medica Holding. For TS index, absolute body temperatures (in degrees Celsius) will be converted to arbitrary units (or scores) using the following scale:  $\leq 37.3^{\circ}C=0$  points;  $37.4-38.0^{\circ}C=1$  point;  $38.1-39.0^{\circ}C=2$  points;  $\geq 39.1^{\circ}C=3$  points.

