# Study design

Study design: multicenter, double-blind, placebo-controlled, parallel-group randomized trial.

The study will enroll patients of either gender aged 18-70 years old with clinical manifestations of ARVI within the first day after the onset of the disease. Signed information sheet for patient will be obtained from all participants prior to the screening procedures. Medical history, concomitant medication, thermometry, patient examination by a doctor, assessment of ARVI symptoms severity will be performed at screening visit.

The nasopharyngeal swabs will be performed for Real-time reverse transcription polymerase chain reaction (PCR) assay to confirm viral etiology of ARVI and to verify respiratory viruses prior to the therapy.

If a patient meets all inclusion criteria and does not have any exclusion criteria, at Visit 1 (Day 1) he/she will be randomized into one of two groups: the 1st group patients will take Anaferon according to the dosage regimen until the end of the study; the 2nd group patients will take Placebo according to Anaferon dosage regimen until the end of the study.

The patients will be provided with a patient diary (paper or electronic) where daily they will record axillary body temperature (using a Geratherm Classic thermometer) and each ARVI symptom severity twice a day (in the morning and in the evening). In addition, antipyretic administration (if applicable) as well as any possible worsening of the patient's condition (if applicable, for safety evaluation/AEs documentation) will also be recorded in a patient diary. An investigator will provide the instructions on filling out the diary and will help the patient to make first records of ARVI symptom severity and body temperature in the diary.

Patients are observed up for 7 days (screening, randomization - 1 day, study therapy - 5 days, follow-up period - 2 days). During treatment and follow-up period two visits are scheduled (at home or at the study site) on days 5 (Visit 2) and day 7 (Visit 3). At Visits 2 and 3, the investigator will carry out physical examination, record dynamics of ARVI symptoms and concomitant therapy and check patient diaries.

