# Inclusion and exclusion criteria

#### Inclusion criteria

- 1. Patients of either gender aged 18-70 years.
- 2. Diagnosis of ARVI based on medical examination: axillary temperature  $\geq$  37.8°C at examination + non-specific/flu-like symptom score  $\geq$ 4, nasal/throat/chest symptom score  $\geq$ 2.
- 3. The first 24 hours after ARVI4 onset.
- 4. Seasonal rise in ARVI incidence.
- 5. Patients giving their consent to use reliable contraception during the study.
- 6. Signed patient information sheet (informed consent form).

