#### Evaluation of sample size

The sample size was assessed on the basis of the following rules and assumptions:

- 1. Statistical provisions.
  - 1.1 the power of the statistical tests " $P = (1 \beta)$ " is assumed to be 80% (the probability of correct rejection of the null hypothesis is 0.8);

- 1.2 the probability of a type I error " $\alpha$ " is allowed to be less than 5% (the probability of the erroneous acceptance of an alternative hypothesis is less than 0.05);
- 1.3 the statistical criteria used are 2-sided;
- 1.4 the calculation of the sample size is based on the assumptions about the expected effects, declared in the primary efficacy endpoint;
- 1.5 the ratio between the sample sizes of the Product and Placebo groups is 1:1 (1 Product patient - 1 Placebo patient);
- 1.6 the significance level for type I error is distributed between primary and secondary endpoints: 0.04 for the primary and 0.01 for the secondary (0.04, 0.01)
- 1.7 statistical hypotheses: null and alternative hypotheses about the superiority of the study drug over placebo using the applied dosing regimen:

primary test:

$$H_0: M_1 - M_2 = 0$$

$$H_a: M_1-M_2 \neq 0$$

where M1 – the median time to resolution of all symptoms in the Product group;

M2 – the median time to resolution of all symptoms in the Placebo group. The sample size is calculated for the Wilcoxon non-parametric test in compliance with the O'Brien-Castelloe approximation.

Programme code:

proc power;

twosamplewilcoxon

vardist("Trt") = normal(5.18,1.36)

vardist("Pl") = normal(5.84,1.28)

variables = "Trt" | "Pl"

nbins=5000

alpha=0.04

npergroup = .

power = 0.8;

run;

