#### Statistical criteria

All the statistical calculations will be performed using two groups of statistical criteria:

- parametric to obtain effective evaluations for parameters of random values, if the relevant conditions of applicability of methods/models are not violated (e.g. sphericity, normality, proportionality of risks, etc.);
- non-parametric in any other cases.

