#### Parametric criteria

The application of parametric criteria will be accompanied by a check for normality of the compared samples (Kolmogorov-Smirnov test).

The following parameters and approaches are to be used:

- To evaluate the differences of continuous variables obtained in one group at two different visits – Student's test for matched samples.
- 2. To evaluate the temporal dynamics of the compared indicators analysis of variance (ANOVA) or covariance (ANCOVA) in the modification with repeated measures.
- 3. In case of multiple comparisons between the groups will apply a variety of corrections for multiplicity (Dunnett), (Tukey), (Scheffe), Holm adaptive test, etc.

<sup>8 On the distribution of the maximum of N independent normal random variables: IID and INID cases. SDSSU Multidisciplinary Research Journal Vol. 1 No. 2, 2013

- 4. In case of abnormal data distribution, approaches with the Generalized Linear Models and / or Mixed Linear Models will be used.
- 5. Selection of the type of distribution, clarification of the factor and covariance structures of the model is carried out with fit statistics such as AIC (Akaike information criterion).

To perform the above-mentioned statistical tests and techniques, it is assumed that the following SAS procedures are used:

- UNIVARIATE check for normality of the compared distributions;
- CORR, MEANS calculation of descriptive statistics;
- TTEST Student t-test with all the modifications;
- GLM analysis of Generalized Linear Models for studying temporal dynamics (ANOVA, ANCOVA);
- GENMOD analysis of Generalized Linear Models.
  MIXED analysis of Generalized Linear Models.

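### The plan gives the Total Severity AUC, its first secondary endpoint, only an unadjusted two-group contrast; naming the pre-randomisation severity score as a covariate would gain precision at no cost

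*Combined protocol and SAP*

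**What the plan says.** - *Secondary endpoints*, item 1: ARVI severity is measured over days 1-6, "based on the area under the curve (AUC) data for the Total Severity (TS) score". Footnote 2 builds the TS score from body temperature and the symptom ratings.
- *Evaluation of sample size*, *Additional test*: the hypotheses concern AUC1 - AUC2, and a two-mean formula uses "the expected difference in the severity AUC between the Product and Placebo groups" and the plain SD of the AUC. No value is given for either.
- *Evaluation of sample size*, items 1.4 and 1.6: the sample size rests on the primary endpoint, and the type I error is divided as 0.04 for the primary and 0.01 for the secondary endpoints.
- *Study design*: "thermometry, patient examination by a doctor, assessment of ARVI symptoms severity will be performed at screening visit". Inclusion criterion 2 sets minimum values for temperature and for both symptom scores, so these are known before randomisation.
- *Parametric criteria*, item 2 and the GLM entry in the SAS list: ANCOVA appears, for the course of indicators over time with repeated measures. No covariate is named. Item 5 leaves model structure to fit statistics such as AIC.
- For non-normal data, *Statistical criteria* prescribes methods that are "non-parametric in any other cases", while *Parametric criteria*, item 4, says: "In case of abnormal data distribution, approaches with the Generalized Linear Models and / or Mixed Linear Models will be used". The *Non-parametric criteria* list includes the Mann-Whitney test.
- The document describes itself as a protocol summary.

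**The concern.** The AUC is the only secondary endpoint with its own hypothesis, yet no section assigns it an analysis model or names baseline severity as a covariate. The one ANCOVA entry is for repeated measures, whereas the AUC is a single value per patient. The Mann-Whitney test takes no covariate.

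The AUC window opens on day 1, so patients who are sicker at entry will plausibly accumulate a larger AUC. If so, part of the between-patient variance can be explained by a score that is already collected, and an unadjusted test leaves it in the error term. This matters somewhat more here because the secondary endpoints share only 0.01 and the trial was not sized for the AUC. Leaving the covariate open also means that it could be chosen after the data are seen.

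**Working it through.** **1. The plan's own figure.** A two-sample Wilcoxon test by the O'Brien-Castelloe approximation, with N(5.18, 1.36) against N(5.84, 1.28), two-sided alpha 0.04 and power 0.80, gives 71 per group (power 80.2%). Then 71/(1 - 0.30) = 101.4, so 102 per group and 204 in total. Both match the plan. The AUC plays no part in these numbers. No sample size for the AUC can be reproduced, because its difference and SD are given only as symbols.

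**2. Inputs for the AUC.**
- From the document: two-sided testing, 1:1 allocation, 0.01 for the secondary endpoints, 71 per arm (expected per-protocol completers) and 102 per arm (upper limit for the Full Analysis Set).
- Assumed: the correlation r between baseline TS score and AUC, from 0 to 0.5; use of the full 0.01 for the AUC; and an effect d of 0.50 SD. That effect size is borrowed from the primary endpoint: (5.84 - 5.18)/sqrt((1.36² + 1.28²)/2) = 0.66/1.321 = 0.50.

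**3. Formulas.** Adjustment multiplies the residual SD, and so the interval width, by sqrt(1 - r²). Power comes from the noncentral t distribution with noncentrality d·sqrt(n/2)/sqrt(1 - r²), on 2n - 2 degrees of freedom unadjusted and 2n - 3 adjusted.

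For n = 71 and d = 0.50, the unadjusted noncentrality is 0.50 × sqrt(35.5) = 2.979 against a critical value of 2.611, giving 64.4%. At r = 0.3 it is 2.979/0.954 = 3.123 against 2.612, giving 69.5%. For n = 102 the unadjusted noncentrality is 0.50 × sqrt(51) = 3.571 against 2.600, giving 83.3%.

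| | Unadjusted | r = 0.2 | r = 0.3 | r = 0.4 | r = 0.5 |
|---|---|---|---|---|---|
| CI width ratio | 1 | 0.980 | 0.954 | 0.917 | 0.866 |
| Power, d = 0.50, 71 per arm | 64.4% | 66.6% | 69.5% | 73.8% | 79.5% |
| Power, d = 0.50, 102 per arm | 83.3% | 85.0% | 87.2% | 90.1% | 93.5% |
| Power, d = 0.40, 71 per arm | 41.3% | 43.2% | 45.7% | 49.7% | 55.7% |
| Power, d = 0.40, 102 per arm | 60.2% | 62.4% | 65.3% | 69.7% | 75.7% |
| Power, d = 0.50, 71 per arm, alpha 0.01/6 | 41.4% | 43.7% | 47.0% | 51.9% | 59.3% |

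The last row splits the 0.01 equally over the six secondary endpoints.

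**4. Downside.** Allowing for chance baseline imbalance (noncentrality divided by sqrt(1 + 1/138) at 71 per arm) lowers the adjusted figures by about 0.4 points. At r = 0 it gives 63.9% against 64.4%, a loss of under 1 point.

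**5. Non-normal route.** This was simulated with 20,000 trials per setting, 71 per arm, alpha 0.01, and a log-normal AUC (log-scale SD 0.6) shifted by 0.50 SD on the log scale. Mann-Whitney power is about 61-62%. Rank ANCOVA (Quade) gives about 64%, 66%, 70% and 76% at r = 0.2, 0.3, 0.4 and 0.5, with type I error of 0.9-1.1%. These are gains in power only.

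**The case against.** **The contrast comes from a sizing formula, not an analysis plan.** This stands. A plain-SD formula is compatible with a later adjusted analysis, so a reader who infers that the plan commits to an unadjusted AUC test goes beyond the text. What the document supports is narrower: this is the only AUC-specific statistical text, and nothing elsewhere adds a covariate.

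**ANCOVA is already listed.** True, and it leaves an adjusted analysis possible. But the entry concerns repeated measures over time, names no covariate and is not tied to the AUC.

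**Nothing is wrong with an unadjusted test.** This stands. A reader might infer bias or an undersized trial, but randomisation makes the unadjusted comparison unbiased, and the sample size rests on the primary endpoint alone.

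**The gain does not fully carry over if normality fails.** This stands. Rank ANCOVA yields a p-value and no interval on the AUC scale, while *Data presentation* asks for confidence intervals. The fallback therefore needs its own interval.

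**The correlation is unknown and may be low.** This stands as a limit on size. The entry minimums narrow the baseline range. If the AUC is taken from the patient diary, a doctor-rated baseline is set against patient ratings, which may also lower r. At r = 0.2 to 0.3 the interval narrows by only 2% to 5%.

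**71 per arm is the smaller analysis set.** Fair. At 0.50 SD and r = 0.5 the gain is about 15 points with 71 per arm (79.5 - 64.4) and about 10 with 102 (93.5 - 83.3). At 0.40 SD it is about 15 points in both.

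**Conclusion.** The point holds as an optional improvement of modest size, not as an error. The document ties no covariate-adjusted model to its first secondary endpoint, although a suitable baseline score is collected before randomisation. Adjustment would narrow the interval by about 2%, 5%, 8% and 13% at r = 0.2, 0.3, 0.4 and 0.5, with corresponding power gains of roughly 2 to 15 points at 0.50 SD and almost no loss if r is zero. These sizes depend on r, the effect size and the use of the full 0.01, none of which the document settles. Because it is a summary, a fuller plan may already name the covariate; the statement here is limited to this text.

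**What to change.** Prespecify for the AUC of the TS score:

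- **Main analysis:** ANCOVA with treatment as factor and the TS score from the pre-randomisation Visit 1 assessment as covariate. The covariate is fixed in advance and exempt from AIC selection. Report the adjusted difference with its confidence interval.
- **Fallback if residual normality fails:** one named method with the same covariate. If rank ANCOVA is chosen, state that it supplies the test only, and still report the adjusted mean difference with a robust or bootstrap interval. If the generalized or mixed model of *Parametric criteria*, item 4, is preferred, name it instead and reconcile it with *Statistical criteria*.
- **Sensitivity analysis:** the unadjusted two-group test.

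The cost is four or five sentences of SAP text and one model statement. No new data, visits or patients are needed, and the sample size does not change.

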#### Primary endpoint (efficacy criterion):

Time to resolution of all symptoms of a clinically diagnosed or PCR-confirmed URI (according to a patient diary).

#### Placebo group:

*Time to resolution of symptoms was estimated on the basis of the previous studies.*  $T_{\rm pl} = (< max(N_t(2.5, 1.47), N_{intox}(5.8, 1.32)>)^7)$ 

Where <...> stands for averaging operation, N(x,s) – normally distributed random variable with the mean x and standard deviation s. Indices: t – fever, intox – intoxication symptoms.

<sup>7 Based on the clinical trial "A study to assess the therapeutic efficacy and safety of Anaferon against influenza and other upper respiratory tract infections in adults". Duration distributions for symptom domains are considered independent. 95% confidence interval is taken for the corresponding standard deviations.

The distribution of the maximum of a number of samples of N normal distributions corresponds to the Gumbel type I distribution

for calculation of the sample size, this empirical distribution is approximated by the normal distribution with characteristics  $m=5.84, \sigma=1.28$ 

# Study drug group:

 $T_{\rm tr} = (\langle max(N(2.6, 1.77), N(5, 1.47)) \rangle)$ 

Where < ... > stands for averaging operation, N(x,s) – normally distributed random variable with the mean x and standard deviation s. Indices: t – fever, intox – intoxication symptoms, cat - catarrhal symptoms. corresponds to the Gumbel type I distribution

for calculation of the sample size, this empirical distribution is approximated by the normal distribution with characteristics m=5.17,  $\sigma=1.36$ .

Therefore, the sample size has been found to be (71) patients in each of the groups (Product and Placebo) to estimate superiority of the study drug over placebo.

Given potential withdrawal of at least 30% subjects ( $C_w=0.3$ ) during the study for various reasons, at least 204 subjects will be required to sign informed consent, 102 per group (see. 1.8).

#### Statistical criteria

All the statistical calculations will be performed using two groups of statistical criteria:

- parametric to obtain effective evaluations for parameters of random values, if the relevant conditions of applicability of methods/models are not violated (e.g. sphericity, normality, proportionality of risks, etc.);
- non-parametric in any other cases.

#### Parametric criteria

The application of parametric criteria will be accompanied by a check for normality of the compared samples (Kolmogorov-Smirnov test).

The following parameters and approaches are to be used:

- To evaluate the differences of continuous variables obtained in one group at two different visits – Student's test for matched samples.
- 2. To evaluate the temporal dynamics of the compared indicators analysis of variance (ANOVA) or covariance (ANCOVA) in the modification with repeated measures.
- 3. In case of multiple comparisons between the groups will apply a variety of corrections for multiplicity (Dunnett), (Tukey), (Scheffe), Holm adaptive test, etc.

<sup>8 On the distribution of the maximum of N independent normal random variables: IID and INID cases. SDSSU Multidisciplinary Research Journal Vol. 1 No. 2, 2013

- 4. In case of abnormal data distribution, approaches with the Generalized Linear Models and / or Mixed Linear Models will be used.
- 5. Selection of the type of distribution, clarification of the factor and covariance structures of the model is carried out with fit statistics such as AIC (Akaike information criterion).

To perform the above-mentioned statistical tests and techniques, it is assumed that the following SAS procedures are used:

- UNIVARIATE check for normality of the compared distributions;
- CORR, MEANS calculation of descriptive statistics;
- TTEST Student t-test with all the modifications;
- GLM analysis of Generalized Linear Models for studying temporal dynamics (ANOVA, ANCOVA);
- GENMOD analysis of Generalized Linear Models.
  MIXED analysis of Generalized Linear Models.

#### Non-parametric criteria

Below, there are the main types of possible comparisons with the respective criteria:

- 1. To evaluate time changes in the parameters compared Friedman test, nonparametric analogue of repeated measures analysis of variance.
- 2. For the frequency analysis of  $2 \times 2$  cross tables  $\chi^2$ -test (if the compared frequencies are greater than 5) or Fisher exact test (if one of the compared frequencies is less than 5).
- 3. For the frequency analysis of cross tables with independent strata Cochran–Mantel– Haenszel test (modification of the  $\chi^2$ -test for multiple comparisons).
- 4. For the frequency analysis of data on the presence / absence of an event or outcome during repeated measures (cross tables with dependent strata) survival analysis.

To perform the above-mentioned non-parametric statistical analysis options, it is assumed that the following SAS procedures are used:

- FREQ Friedman test,  $\chi^2$ -test and / or Fisher exact test; Cochran–Mantel–Haenszel test
- LIFETEST, PHREG survival analysis
- NPAR1WAY Mann-Whitney U-test.

#### Safety parameters

Adverse events recorded during the study will be grouped into frequency tables by severity, seriousness and relationship with the study drug.

#### Data presentation

Descriptive statistics will be provided for each study continuous / interval variable. Numerical data will be presented by mean, standard deviation, min and max values. Relevant confidence intervals will also be provided for the data suggesting statistical conclusion. Extreme values (outliers) will be analyzed additionally. The data will be grouped by visits. The categorical variables will be presented as frequency tables by visits.

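### The primary hypothesis is about median time to resolution, but the only presentation rule lists no median, and an ordinary mean cut off at about Day 7 does not estimate the planned 0.66-day difference

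*Combined protocol and SAP*

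**What the plan says.** All references are to the combined protocol and SAP.

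- **Hypothesis.** The section *Evaluation of sample size*, item 1.7, writes the primary test as M1 - M2, where M1 is "the median time to resolution of all symptoms in the Product group" and M2 is the placebo counterpart. The trial is sized for a Wilcoxon test. Of the type I error, the plan assigns "0.04 for the primary and 0.01 for the secondary", and "the statistical criteria used are 2-sided".
- **Presentation.** The section *Data presentation* covers every continuous or interval variable: "Numerical data will be presented by mean, standard deviation, min and max values". It adds: "Relevant confidence intervals will also be provided for the data suggesting statistical conclusion". Neither the parameter nor the level of these intervals is named.
- **Length of observation.** The section *Study design* says: "Patients are observed up for 7 days". The schedule of procedures puts Visit 3 at Day 7 ± 1. The endpoint is timed from enrollment, which is Day 1.
- **Survival methods.** The section *Non-parametric criteria* lists LIFETEST and PHREG. It describes survival analysis only for presence or absence of an event over repeated measures and does not assign it to the primary endpoint.
- **Unresolved patients.** The second secondary endpoint is the percentage of patients with resolution, so the plan expects some not to resolve. It does not say how they enter a summary of resolution times.

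**The concern.** The plan tests one quantity and, by its stated rule, describes another. With complete, roughly normal data this would matter little, because mean and median nearly coincide. Here a patient unresolved at the last visit has no observed time. An ordinary mean must leave that patient out or put in the cutoff. More placebo than active patients are expected to be unresolved, so both choices pull the arms together. The SD shrinks as well, and the maximum tends to the end of observation. The report could then pair a p-value with an effect size that is not the one the trial was planned on. An interval at the customary 95% level would also not match a test at 0.04.

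**Working it through.** **Inputs.** Active arm Normal(5.18, 1.36) and placebo Normal(5.84, 1.28) days, two-sided alpha 0.04 and power 0.80, all from the section *Evaluation of sample size*. Withdrawal is 30%, from the section *Study drug group*. The planned difference is 5.84 - 5.18 = 0.66 days.

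**Step 1: reproduce the plan's figure.** In the O'Brien-Castelloe approximation with 5000 bins, the odds are 1.763, the null SD term is 2.309 and the alternative SD term is 2.378. Then

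N = [(2.054 × 2.309 + 0.842 × 2.378) / ln 1.763]² = 141.4,

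or 70.7 per group, rounded up to 71. Next, 71 / 0.7 = 101.4, so 102 per group and 204 in total. This matches the plan.

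**Step 2: means under a cutoff T.** Let z = (T - m)/s, with φ and Φ the standard normal density and distribution function.

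- Resolved patients only: m - s·φ(z)/Φ(z)
- Unresolved patients set to T: m - s·[φ(z) - z(1 - Φ(z))]

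At T = 7:

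- Active: z = 1.338, φ = 0.1629, Φ = 0.9096. Resolved only: 5.18 - 1.36 × 0.1629/0.9096 = 4.94. Capped: 5.18 - 1.36 × (0.1629 - 1.338 × 0.0904) = 5.12.
- Placebo: z = 0.906, φ = 0.2646, Φ = 0.8176. Resolved only: 5.84 - 1.28 × 0.2646/0.8176 = 5.43. Capped: 5.84 - 1.28 × (0.2646 - 0.906 × 0.1824) = 5.71.

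The differences are 0.49 and 0.59. The capped SDs are 1.26 and 1.08, against the planned 1.36 and 1.28.

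**Step 3: range over the cutoff.** The plan does not fix the number of elapsed days. Day 7 counted from enrollment on Day 1 is about 6 elapsed days, and the 24-hour confirmation of normal temperature could remove another.

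| Elapsed days | Unresolved, active / placebo | Difference, resolved only | Difference, capped |
|---|---|---|---|
| 5 | 55% / 74% | 0.25 (62% below 0.66) | 0.26 (61% below) |
| 6 | 27% / 45% | 0.36 (45% below) | 0.45 (31% below) |
| 7 | 9% / 18% | 0.49 (26% below) | 0.59 (11% below) |
| 8 | 2% / 5% | 0.60 (10% below) | 0.65 (2% below) |

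**Step 4: can the median be estimated?** At 7 or 8 days both planning medians (5.18 and 5.84) lie well before the cutoff. At 6 days the chance that a placebo patient has resolved is 0.550. With 71 patients and no earlier censoring, the Kaplan-Meier median is not reached when at most 35 resolve, which has binomial probability 0.20. Its upper confidence limit is undefined when at most 43 resolve, probability 0.86 (the same at 95% and 96%). At 5 days neither planning median is reached.

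**Step 5: is the test harmed?** Simulated Wilcoxon power at 71 per group, with unresolved patients tied at the cutoff, is 0.80 at 8 days, 0.79 at 7 and 0.78 at 6, against 0.80 without a cutoff. It would be 0.71 if only 5 days were usable.

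**The case against.** The presentation rule reads as a generic descriptive rule. It groups data by visit, which suits vital signs and symptom scores better than a single time per patient, and it also promises confidence intervals. Survival procedures are listed, and LIFETEST can estimate medians. A reader might therefore infer from the finding that the plan rules out reporting a median. The documents do not support that: they are silent, not prohibitive. What remains is that no sentence commits to the median or to any other effect measure for the primary endpoint, and the one rule that does apply to continuous variables leaves it out.

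A reader might also infer that every mean is biased here. That is too strong. With a common cutoff and no earlier dropout, the capped mean is a restricted mean, and 0.59 days at T = 7 is a correct value for that quantity. It misleads only if presented as the mean resolution time or compared with 0.66. The shortfall also depends on a cutoff and a handling rule that the plan does not state, and at 8 days it is small.

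Finally, the median is no complete answer. Step 4 shows that it can fail at 6 days. Diaries are filled in twice daily, so medians will be coarse: if times are assigned to the end of each half-day, 5.18 and 5.84 become 5.5 and 6.0, a difference of 0.5. This objection stands and shapes the fix.

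**Conclusion.** The concern holds as a gap in estimation and reporting. The hypothesis names a median, the stated summary rule omits it, and no effect measure suited to incomplete follow-up is assigned to the primary endpoint. On the planning distributions, an ordinary mean difference would fall below 0.66 days by 11% to 26% at 7 elapsed days, 31% to 45% at 6, and 2% to 10% at 8. These figures assume the plan's normal distributions, one cutoff for all patients, no earlier dropout, and one of two ways of handling unresolved patients.

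It would be wrong to conclude that the sample size or the test is faulty. The 71 per group reproduces, and power barely moves at 6 to 8 elapsed days. The minimum is not distorted by the cutoff.

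**What to change.** For the primary endpoint and secondary endpoint 3, replace mean, SD, minimum and maximum with the following:

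1. Kaplan-Meier estimates by arm, with patients unresolved at their last observation treated as censored.
2. The median per arm, where reached.
3. As a prespecified between-arm effect measure, the difference in restricted mean time to resolution up to a named day within the observation period. It remains estimable when a median is not reached.
4. 96% confidence intervals for the primary endpoint, to match the 0.04 test.

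Keep mean and SD for variables that are fully observed.

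The cost is a few sentences in the section *Data presentation*, and LIFETEST is already listed. There are three drawbacks. The median or its upper limit may be unavailable if only about 6 elapsed days are usable. Twice-daily diary entries make the medians coarse. The restricted mean difference is smaller than 0.66 days by construction, so the report should say so and not set it against the planning figure as if the two were the same quantity.
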